8.5.2 Leukapheresis

Collection of PBMC via leukapheresis will be performed in accordance with the standard practices of the participating apheresis center. Ideally, in this procedure, approximately 1.5 liters of blood will be processed over about 1 hour using

peripheral veins for venous access. The blood will be anti-coagulated in accordance with standard practice of the apheresis center.

Post-procedural safety assessments will be performed in accordance with the standard practices of the participating apheresis center. Additionally, the participant will be advised to contact the study site if they experience any adverse events following the procedure.

Eligibility for leukapheresis:

- Prior to leukapheresis, participant must meet all apheresis center requirements for this procedure.
- Participants who can become pregnant must have a negative pregnancy test within 48 hours prior to the procedure.

8.6 Extended follow-up for participants with unresolved study product-related urticaria-associated symptoms

Participants with unresolved study product-related urticaria-associated symptoms (eg; wheal and flare lesions, pruritis, and/or erythematous lesions) at Visit 15 (month 12) will be asked to have follow-up remote contacts (eg, via phone) with CRS staff until all associated signs and symptoms resolve, or for up to an additional 48 months (4 years) after the month 12 visit, whichever time is shorter (see HVTN 302 SSP for detail). In addition, participants will come into the clinic for serum collections for banking at the following times (See [Appendix C](#)):

- Visit 102
- At clinic visit(s) scheduled in response to a urticaria-associated symptom. This can be multiple visits for a single flare or during recurrent visits for multiple flares.
- Participant's exit visit

A sample addendum informed consent form is provided in [Appendix G](#). Participants who consent for this extended follow-up period will follow the schedule of visits and evaluations shown in [Appendix C](#).

CRS staff will record the following:

- Updates on dermatological AEs deemed related to study product;
- New or updates to current concomitant medications;
- A brief urticaria-related symptom questionnaire;

- New SAEs, regardless of attribution to study product;
- New dermatological AEs, regardless of attribution to study product; and
- Targeted physical exam findings (if a physical exam is conducted).

Resolution of symptoms that would allow for termination of extended follow-up are defined as the following:

- For participants not taking antihistamines prior to enrollment (aka baseline): absence of study product-related urticaria-associated symptoms (eg; wheal and flare lesions, pruritis, and/or erythematous lesions) while off antihistamines for at least 8 weeks. The HVTN 302 PSRT will be consulted prior to terminating a participant from study follow-up.
- For participants taking antihistamines for pre-existing allergic conditions prior to enrollment (aka baseline): back-to-baseline dosage of antihistamines, with lack of wheal and flare lesions and/or pruritic, erythematous lesions for at least 8 weeks. The HVTN 302 PSRT will be consulted prior to terminating a participant from study follow-up.

8.7 Visit procedures, schedule, windows and missed visits

The schedule of visits and evaluations performed at each visit are shown in [Appendix A](#) (for participants undergoing LN FNA and/or leukapheresis) and [Appendix B](#) (for participants undergoing neither LN FNA nor leukapheresis) and Appendix C (for participants in extended follow-up). Visit windows are shown in [Appendix D](#) and [Appendix E](#). The procedures for documenting missed visits and out-of-window visits are described in the HVTN 302 SSP. If the missed visit is one that required safety assessments or local safety labs, HVTN CRS staff should attempt to bring the participant in for an interim visit as soon as possible.

8.8 Monitoring for HIV infection

Study participants will be tested for HIV infection periodically throughout the study as indicated in the schedules included in [Appendix A](#) and [Appendix B](#). The Laboratory Program (or approved diagnostic laboratory) will follow the HVTN HIV testing algorithm (see HVTN Laboratory Center MOP) which is able to distinguish vaccine-induced antibody responses from actual HIV infections. Participants will be promptly informed and counseled if they become HIV-infected during the study and referred for treatment (see Section [5.2.2](#)).

Study participants will receive regularly scheduled counseling regarding avoidance of HIV infection in accordance with the most recent Centers for Disease Control and Prevention HIV counseling guidelines.

Although the study vaccine will not cause HIV infection, it may induce antibodies detectable by standard HIV infection screening techniques. This is referred to as vaccine induced seropositivity (VISP). The following steps will be taken to protect participants from adverse consequences associated with VISP:

- Participants will be counseled to avoid HIV antibody testing outside of the HVTN CRS during study participation.
- Participants can receive HIV diagnostic testing from the CRS following their last scheduled visit until they are told they do not have VISP.
- Participants with VISP will be offered poststudy HIV diagnostic testing (per the HVTN poststudy HIV testing algorithm) periodically free of charge as medically/socially indicated (approximately every 6 months) unless or until HIV antibody testing is no longer standard in clinical settings.
- Unless they request that their names be removed, the names of all participants in HVTN studies are entered into a secure VISP registry in order to verify that an individual received an HIV vaccine (and therefore has the potential for VISP) and to qualify former participants for post-study HIV testing to distinguish between VISP and HIV infection. Information in the VISP registry is not used for research.

8.9 Early termination visit

If a participant terminates participation in the study early for any reason, the site principal investigator should consider if the following assessments are appropriate: end-of-study HIV test, CBC with differential, serum chemistry (ALT and creatinine), physical examination, social impact assessment, and if indicated, a pregnancy test (see [Appendix A](#) and [Appendix B](#)). If the site principal investigator has questions regarding a termination visit, they should consult with the PSRT.

For participants with HIV infection, please see Section [5.2.2](#). If the site principal investigator has questions regarding a termination visit, they should consult with the PSRT.

Early termination to extended follow-up consider all study procedures and sample collection in [Appendix C](#).

9 Safety and adverse events

9.1 Adverse events

Unsolicited AEs will be collected over a period of 30 days after each vaccination. All collected AEs are captured in the clinical database on the appropriate CRF. Clinic staff should evaluate every AE to determine if (1) the AE meets the requirements for expedited reporting (see Section 9.3.1), (2) if the AE meets the criteria for a safety pause/prompt AE review (see Section 9.7), (3) if the AE meets the criteria for an MAAE, and (4) if the AE is an adverse event of special interest (AESI). Reportable AESIs will be myocarditis and pericarditis.

In addition, a limited set of AEs will be collected and reported through the end of the main study.

- SAEs/expedited adverse events (EAEs)
- MAAEs (defined as any adverse events leading to an unscheduled visit to a healthcare professional)
- AEs leading to early participant withdrawal or early discontinuation of study vaccine(s) administration.
- Adverse Events of Special Interest (AESIs):
 - myocarditis
 - pericarditis
- Participants in the Extended Follow-up (see Section 8.6) will have this subset of AEs collected and reported through the end of their study participation:
 - New dermatologic AEs (indicate if an MAAE)
 - SAEs

Adverse events (AEs) will be graded according to the Division of AIDS (DAIDS) Table for Grading the Severity of Adult and Pediatric Adverse Events, Corrected Version 2.1 – July 2017 (<https://rsc.niaid.nih.gov/clinical-research-sites/daids-adverse-event-grading-tables>), with the following exceptions:

- Unintentional Weight Loss is required to be reported as an AE only if it is considered to be potentially deleterious to the participant's health (see HVTN 302 SSP);

- Creatinine is required to be reported as an AE only if it is gradable per the increase from local lab ULN parameter. Do not grade elevated creatinine based on the change from the baseline parameter.
- Do not grade creatinine clearance or eGFR based on the change from the baseline parameter. Do not grade on the basis of eGFR if there is clinical concern for kidney injury.
- Injection Site Erythema or Redness and Injection Site Induration or Swelling will not consider surface area and interference with usual social and functional activities such that:
 - Grade 1 is: 2.5 to < 5 cm in diameter;
 - Grade 2 is: ≥ 5 to < 10 cm in diameter;
 - Grade 3 is: ≥ 10 cm in diameter OR ulceration OR secondary infection OR phlebitis OR sterile abscess OR drainage;
 - Grade 4 is: Potentially life-threatening consequences (eg, abscess, exfoliative dermatitis, necrosis involving dermis or deeper tissue);

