Rare risks with any injection procedure include infection at the site of injection. Signs of infection at the injection site include severe pain, erythema, induration, warmth or drainage. There are rare reports of anaphylaxis with many vaccines. There may be side effects from the study products which may be serious or life threatening that we do not know about yet.

If antibodies elicited by the study vaccine result in a positive or indeterminate HIV test (ie, vaccine-induced seropositivity or VISP), this may have a negative impact on employment, health care, insurance, travel, and personal relationships. HIV polymerase chain reaction (PCR) will be used to exclude or confirm HIV infection.

Blood drawing may cause pain, bruising, fainting, and, rarely, infection at the site where the blood is taken. Leukapheresis can also cause pain, bruising, and, rarely infection. Additional risks may depend on local leukapheresis procedures. Fainting can also occur, but occurs less frequently than with blood drawing.

Fine needle aspiration of lymph nodes can uncommonly cause pain, bruising, and/or bleeding at the site where the needle is inserted. Similar to any procedure where a needle is inserted into the skin (such as vaccination, as described above), there is a rare risk of localized infection. The local anesthetic rarely can cause temporary arm numbness or weakness.

Risks during Pregnancy: Because possible effects of the study vaccine on a fetus or nursing infant are unknown, persons assigned female sex at birth who have

reproductive potential will be tested for pregnancy at screening and prior to administration of each dose of study vaccine. Such persons will be asked to notify the site immediately if they suspect or learn they are pregnant during this study. In case of pregnancy, participants will continue to be followed for safety and the participant will not receive any additional vaccinations. The participant will be contacted about the outcome of a pregnancy that begins during the study.

Other Risks: The medical tests performed as part of this research protocol may result in new diagnoses or abnormal values without clinical significance.

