3.1 Primary objectives and endpoints

Primary objective 1:

To evaluate the safety and tolerability of BG505 MD39.3 trimer mRNA vaccines in healthy, HIV-uninfected adults

Primary endpoint 1:

Local and systemic reactogenicity signs and symptoms for a minimum of seven days following receipt of any study product. Laboratory measures of safety. All adverse events (AEs) for thirty days after receipt of study vaccination

All serious adverse events (SAEs), medically attended adverse events (MAAEs), adverse events of special interest (AESIs), and AEs leading to early participant withdrawal or permanent discontinuation will be collected throughout the study

Primary objective 2:

To evaluate the ability of BG505 MD39.3 trimer mRNA vaccines to elicit autologous neutralizing antibodies and to compare responses between the membrane-bound vaccine regimen (BG505 MD39.3 gp151 mRNA) and the membrane-bound knockout (BG505 MD39.3 gp151 CD4KO mRNA) and between the membrane-bound vaccine regimen (BG505 MD39.3 gp151 mRNA) and the soluble trimer (BG505 MD39.3 mRNA) vaccine arms, within each dose level

Primary endpoint 2:

Occurrence, magnitude, and response rate of serum antibody neutralization of a vaccine-matched tier 2 HIV-1 strain as measured by the TZM-bl assay two weeks after the third vaccination

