8.5.1 Lymph node FNA

Tissue sampling of an axillary lymph node ipsilateral to the deltoid injection site will be carried out percutaneously by FNA. Lymph node FNA will not be performed if the injection is given in the thigh. This procedure will be performed in accordance with the standard practices of the participating provider and/or facility. The procedure involves tissue retrieval with a needle via a small skin incision under sonographic guidance. Approximately 2-4 passes will be made to retrieve cytologic material.

Post-procedural safety assessments will be performed in accordance with the standard practices of the participating provider and/or facility. The participant will be advised to contact the study site if they experience severe pain, fever (post-procedural body temperature $\geq 38.0^{\circ}\text{C}$ or 100.4°F) or other evidence of infection (inflammation and/or pus) at the aspiration site, or arm numbness or weakness.

Eligibility for lymph node FNA:

- Participant may not be taking warfarin, oral antithrombin equivalents (including, but not limited to, apixaban, rivaroxaban, dabigatran), enoxaparin injections, or other medications that would increase the risk of bleeding as assessed by the clinician performing the procedure.
- The vaccine injection was given in the deltoid and there is no evidence of localized infection directly superior to the axillary aspiration site
- No other contraindication to procedure as assessed by the clinician performing the procedure
- Participants who can become pregnant must have a negative pregnancy test within 48 hours prior to the procedure.

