Appendix D Visit windows for main study

Visit Number	Visit Type	Lower Allowable Window (-)	Lower Target Window (-)	Target Day ¹	Upper Target Window (+)	Upper Allowable Window (+)
01.0	Screening	-56	-		-	Up to Day 1
02.0	Enrollment/Vaccination 1	-	-	1	-	-
03.0	1 week post-vaccination 1		-3	8	+2	
04.0	2 weeks post-vaccination 1		-4	15	+4	+7
05.0**	6 weeks post-vaccination 1 FNA	-7	-4	43	+4	+7
06.0	Vaccination 2	-7	-4	57	+4	+7
07.0	1 week post-vaccination 2		-3	64	+2	
08	2 weeks post-vaccination 2	-	-4	71	+4	+7
	Leukapheresis		-4	71	+1	+4
09.0**	4 weeks post-vaccination 2 FNA	-7	-4	85	+4	+7
10.0	Vaccination 3	-21	-14	169	+14	+21
11.0	1 week post-vaccination 3		-3	176	+2	
12.0	2 weeks post-vaccination 3 Primary Immunogenicity		-4	183	+4	+7
	Leukapheresis		-4	183	+1	+4
13.0**	4 weeks post-vaccination 3 FNA	-7	-4	197	+4	+7
14.0	8 weeks post-vaccination 3	-14	-7	225	+7	+14
15.0	Final Visit	-28	-14	365	+14	+28

Green shading = Vaccination Visit; Blue shading = FNA visit

* All target dates are relative to Day 1, with the exception of the post-vaccination visits (visits 3.0-5.0, 7.0-9.0, and 11.0-14.0) which are relative to the vaccination immediately preceding the visit.

** Visits 5.0, 9.0, and 13.0 are only required for participants who are providing lymph node FNA collections.

Appendix E Visit windows for follow-up of participants with unresolved study product-related urticaria-associated symptoms

Visit Number	Visit Type	Lower Allowable Window (-)	Lower Target Window (-)	Target Day*	Upper Target Window (+)	Upper Allowable Window (+)
101	Initial contact	-42	-28	456	+28	+42
102	1.5-year contact	-42	-28	547	+28	+42
103	1.75-year contact	-42	-28	638	+28	+42
104	2-year contact	-42	-28	729	+28	+42
105	2.5-year contact	-84	-56	911	+56	+84
106	3-year contact	-84	-56	1093	+56	+84
107	4-year contact	-84	-56	1457	+56	+84
108	Final 5-year contact	-84	-56	1821	+56	+84

* All Target Days are relative to Day 1 of the main study (enrollment date); informed consent for follow-up can be collected any time prior and up to Visit 101

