11 SAFETY TABLES, PARTICIPANT LISTINGS, AND FIGURES

11.1 List of Tables

The following tables are included in the SMB reports and FSR for Safety:

- Enrollment Report
- Demographics and Vaccination Frequencies
- Overall Protocol Status
- Maximum Local and Systemic Reactogenicity Summaries
- Adverse Experiences by Body System and Severity – By Decreasing Frequency
- Adverse Experiences by Preferred Term and Severity – By Decreasing Frequency – Includes Severe, Life-threatening or Fatal Experiences Only
- Adverse Experiences by Preferred Term and Severity – By Decreasing Frequency – Includes Experiences of All Severities
- Adverse Experiences by Preferred Term and Relationship to Study Product – By Decreasing Frequency – Includes Related Experiences Only
- Adverse Experiences by Preferred Term and Relationship to Study Product – By Decreasing Frequency – Includes Experiences of Any Relationship
- Expedited Adverse Experiences (EAEs) Reported to the Regulatory Support Center (RSC)
- Pregnancy Listing

Additional tables included in the FSR for Safety:

- Social Impact Summary
- FNA/Leukapheresis Related Events
- Listing of Urticaria Adverse Events
- End of Study Diagnostic Testing Results for Vaccinees
- Local Lab Value Summary Statistics
- Local Laboratory Values Meeting Grade 1 AE Criteria or Above

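### No adverse-event period is tied to the lymph node FNA, so most follow-up time after FNA falls outside all-AE collection and the planned procedure table may understate FNA events

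*Protocol*

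**What the plan says.** Protocol section 9.1 anchors general collection to dosing: "Unsolicited AEs will be collected over a period of 30 days after each vaccination". Primary endpoint 1 in section 3.1, repeated in SAP section 4, uses the same period: "All adverse events (AEs) for thirty days after receipt of study vaccination".

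Beyond that period, section 9.1 continues: "In addition, a limited set of AEs will be collected and reported through the end of the main study". The set is SAEs and expedited events, medically attended events, events of special interest (myocarditis and pericarditis), and events leading to withdrawal or to stopping the vaccine. The medically attended class is broad: "MAAEs (defined as any adverse events leading to an unscheduled visit to a healthcare professional". It therefore includes non-serious events.

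Appendix D lists Visit 5 as "6 weeks post-vaccination 1 FNA", target Day 43. The other two FNAs (Visits 9 and 13) are four weeks after doses 2 and 3, at Days 85 and 197. Leukapheresis is two weeks after doses 2 and 3.

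On the risks, section 2.8.1 says: "Fine needle aspiration of lymph nodes can uncommonly cause pain, bruising, and/or bleeding at the site where the needle is inserted". It adds that local infection and temporary arm numbness or weakness are rare. Section 8.5.1 leaves post-procedure assessment to facility practice and says: "The participant will be advised to contact the study site if they experience severe pain, fever". That list goes on to other signs of infection and to arm numbness or weakness. Section 8.5.2, on leukapheresis, instead asks participants to report any adverse event.

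SAP section 11.1 lists a table titled "FNA/Leukapheresis Related Events" for the final safety report. It gives no source, time window, attribution rule or denominator.

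**The concern.** A window that starts at vaccination suits the vaccine safety endpoint. It need not suit an invasive research procedure done weeks later. Here the first FNA comes after the window has closed, the other two come near its end, and leukapheresis sits in the middle of it.

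If section 9.1 is followed as written, a bruise or bout of pain after FNA that leads to no unscheduled healthcare visit has little or no place to be recorded. The same event after leukapheresis would be recorded. The SAP then puts both procedures in one table, so a reader could take a difference in ascertainment for a difference in safety. About half of the 54 Part A participants are expected to have FNA, each up to three times: roughly 27 people and at most about 81 procedures.

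**Working it through.** **Inputs.** Appendix D target days: doses on Days 1, 57 and 169; FNA on Days 43, 85 and 197; leukapheresis on Days 71 and 183. Permitted windows: FNA −7/+7 days; leukapheresis −4/+4 days. All-AE period: 30 days after each dose (section 9.1), counted here as days 0 to 30.

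**1. Reproduce the plan's labels.** 43 − 1 = 42 days (6 weeks); 85 − 57 = 28 days (4 weeks); 197 − 169 = 28 days (4 weeks). All agree with Appendix D. For leukapheresis, 71 − 57 = 14 and 183 − 169 = 14.

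**2. Collection left after each procedure** = 30 − days since the preceding dose.

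| Procedure | Days since dose, target (permitted) | All-AE days left, target (permitted) |
|---|---|---|
| FNA 1 | 42 (35 to 49) | −12 (−5 to −19) |
| FNA 2 and FNA 3 | 28 (21 to 35) | 2 (9 to −5) |
| Leukapheresis, both | 14 (10 to 18) | 16 (20 to 12) |

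A negative figure means the window closed that many days before the procedure.

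**3. Does the dose-2 window rescue FNA 1?** At target it opens 57 − 43 = 14 days after FNA 1. Over permitted dates, FNA 1 is on Days 36 to 50 and dose 2 on Days 50 to 64, so the gap runs from 0 to 28 days.

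**4. Share of follow-up time outside, at target dates.** The documents give no period of interest, so these are assumptions.
- 14 days (days 0 to 13 after each FNA): inside are 0 + 3 + 3 = 6 of 42 days, so 36 of 42 (86%) are outside.
- 7 days including the procedure day (days 0 to 6): 6 of 21 inside, 15 of 21 (71%) outside.
- 7 days after the procedure day (days 1 to 7): 0 + 2 + 2 = 4 of 21 inside, 17 of 21 (81%) outside.
- Leukapheresis, 14 days: days 14 to 27 after dosing, so 28 of 28 inside. On the latest permitted date the span is days 18 to 31, so 13 of 14 are inside.

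**5. Share of events, as opposed to time.** Assume equal numbers of events per FNA, all starting within 13 days, and let q be the fraction starting 3 to 13 days after the procedure. At target dates the share outside is 1/3 + (2/3)q: 33% at q = 0, 50% at q = 0.25, 100% at q = 1. If every event starts on the procedure day but FNA 2 and FNA 3 are spread evenly over days 24 to 32 (target window), it is 1/3 + (2/3)(2/9) = 48%. Over days 21 to 35 (permitted window) it is 1/3 + (2/3)(5/15) = 56%.

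**6. Next scheduled visit after each FNA, at target.** FNA 1: 57 − 43 = 14 days. FNA 2: 169 − 85 = 84 days. FNA 3: 225 − 197 = 28 days.

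**The case against.** A reader might infer that most FNA harms will go unrecorded and that the SAP table will understate them. The documents do not support that, for four reasons.

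- Section 2.8.1 gives no onset times or rates, and the harms it names are mainly at the needle site. If all begin within 2 days and visits are on target, one third fall outside collection. A majority requires more than a quarter to start later, or FNA 2 and FNA 3 to be done late in their windows.
- It would be wrong to say that non-serious events are collected for 30 days and no longer. Medically attended events and those leading to withdrawal or vaccine discontinuation run to the end of the main study. An FNA complication that prompts an unscheduled healthcare visit is captured.
- The SAP names the table by title alone, so its source cannot be inferred.
- Appendix A has a general AE row separate from its MAAE/AESI/SAE row. The general row appears ticked at the FNA visits, although the extracted columns are partly broken. Ticks at later visits do not prove that section 9.1 limits that row. Visit 10 is a vaccination visit, and Visit 14 may be the first chance to record events up to day 30 after dose 3. The apparent tick at Visit 15, 365 − 169 = 196 days after dose 3, is harder to square with a 30-day rule.

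It is also fair that facility practice provides some assessment after the procedure, that the contact list in section 8.5.1 covers infection and arm numbness or weakness, and that no formal comparison of FNA with leukapheresis is planned.

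These points limit the claim but leave the gap open. An AE tick at an FNA visit falls on the procedure day and does not create follow-up afterwards. At best, section 9.1 and Appendix A do not sit clearly together.

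**Conclusion.** The gap is real and follows from the plan's own dates. FNA 1 lies after the dose-1 window on every permitted date. FNA 2 and FNA 3 keep about 2 days at target, and from 9 days to none across their windows. Leukapheresis keeps 12 to 20 days. Most post-FNA follow-up time is outside all-AE collection: 86% on an assumed 14-day period, and 71% or 81% on 7 days depending on how the procedure day is counted.

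The supported conclusion is that non-serious, non-medically-attended FNA events may be missed, and that the procedure table may understate FNA events relative to leukapheresis. The share of events lost cannot be given without onset times. The vaccine safety endpoint is not undermined, since its window is rightly anchored to dosing. This is a worthwhile, inexpensive improvement to procedural safety reporting.

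**What to change.** - **Section 9.1:** for participants having FNA or leukapheresis, also collect all AEs for a fixed period after each procedure (for example 7 or 14 days), regardless of time since vaccination. Ask about them at the next scheduled visit. A remote contact is optional, and would help most after FNA 2, where that visit is 84 days away.
- **Appendix A and sections 8.5.1 and 8.5.2:** reconcile the AE row, and the differing wording on when participants contact the site, with that rule.
- **SAP section 11.1:** base the procedure table on the per-procedure period, state its source and attribution rule, and use procedures performed as the denominator.
- **If the procedures are already complete:** define the table's source and window, and report the unequal ascertainment of FNA and leukapheresis as a limitation.

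The cost is slightly more mild events recorded and a small change to data collection. If a remote contact follows every FNA, that is at most about 27 × 3 = 81 short contacts; after FNA 2 alone, about 27.

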10.2 Analyses to investigate related urticaria adverse events

The following analyses will be conducted to generate potential explanations of the related urticaria adverse events observed in HVTN 302.

Urticaria cases are defined as participants who report any adverse event of urticaria (medDRA preferred term) of any duration deemed related to study product. Urticaria non-cases are defined as participants who do not report any such event.

Differences in baseline variables identified by the HVTN 302 protocol team leadership will be formally compared between urticaria cases and non-cases by Barnard's exact test for the following 15 binary variables at enrollment: female sex at birth, Hispanic or Latino ethnicity, race = White given data sparsity, history of eczema, history of seasonal and environmental allergies, history of food allergies, history of drug allergies, history of other and non-specified allergies, and use of antihistamine/asthma inhaler/steroid medications, COVID-19 infection, mRNA COVID-19 vaccination (Moderna or Pfizer), any Moderna COVID-19 vaccination, any Pfizer COVID-19 vaccination, Moderna received as last COVID-19 vaccination, Pfizer received as last COVID-19 vaccination. The Wilcoxon rank sum test will be used to evaluate differences in distribution of age in years at enrollment between urticaria cases and non-cases. Multiplicity adjustment of the p-values for comparing each of these 16 demographic characteristics and prior histories between participants with and without urticaria will be done to control the family-wise error rate at 0.05 using Holm, 1979 adjustment. For covariates where the unadjusted p-value was less than 0.05 for the association with urticaria, odds ratios (OR) and nominal 95% CIs were calculated by median-unbiased estimation (mid-p) method [1] with Haldane-Anscombe correction for 0 counts [2].

Tables

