- Demographics (sex at birth, ethnicity, race, age in years), prior conditions and use of allergy medications (history of eczema, history of seasonal and environmental allergies, history of food allergies, history of drug allergies, history of other and non-specified allergies, use of antihistamine/asthma inhaler/steroid medications at enrollment), Covid-19 infection prior to enrollment, receipt of any Covid-19 mRNA vaccination prior to enrollment, receipt of any Moderna Covid-19 mRNA vaccination prior to enrollment, receipt of Moderna as last Covid-19 mRNA vaccination prior to enrollment. Stratified by urticaria case/non-case status, summarized by n/N, % for binary/categorical variables and by 25%, median, 75% for age in years.
- Covid-19 vaccination post-enrollment stratified by urticaria case/non-case status, summarized by n/N (%).

Figures

- Timeline of vaccination times (grey open circles), blood draws (red points), and urticaria AE onset and resolution (salmon line segments or arrows if no resolution) for urticaria cases where x-axis denotes study weeks from enrollment and y-axis denotes ptid (study group).
- Boxplots of days from last mRNA Covid-19 vaccination to enrollment for urticaria cases and non-cases, with different point types denoting Pfizer (triangle) vs. Moderna (filled circle) vaccine.
- Boxplots of days from last Moderna Covid-19 vaccination to enrollment for urticaria cases and non-cases.
- Spaghetti plots of eosinophil and basophil counts over time with red lines denoting urticaria cases and grey dashed lines indicating non-cases.

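### Beyond 30 days after a dose, the main study does not list new dermatologic AEs for collection, so a late, unattended first urticaria can be analysed as a non-case in SAP 10.2

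*Protocol*

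**What the plan says.** **Main-study collection.** Protocol Section 9.1: "Unsolicited AEs will be collected over a period of 30 days after each vaccination". The primary safety endpoint in Section 3.1 uses the same window: "All adverse events (AEs) for thirty days after receipt of study vaccination". For the rest of the main study, Section 9.1 says: "In addition, a limited set of AEs will be collected and reported through the end of the main study". The set has four parts:

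- SAEs and expedited AEs
- medically attended AEs (MAAEs), meaning those that lead to an unscheduled healthcare visit
- AEs leading to withdrawal or to early discontinuation of vaccination
- AESIs, which are myocarditis and pericarditis only

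**Extended follow-up.** For participants who enter the extension, Section 9.1 adds skin events, whether or not they are attended (listed as "New dermatologic AEs (indicate if an MAAE"). Section 8.6 opens the extension to those with unresolved product-related urticaria symptoms at Visit 15 (Month 12). It expects repeat episodes and says of symptom-driven clinic visits: "This can be multiple visits for a single flare or during recurrent visits for multiple flares".

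**Schedules.** Appendices A and B carry a general adverse-event row, separate from the row for MAAEs, AESIs and SAEs.

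**Analysis.** SAP Section 10.2: "Urticaria cases are defined as participants who report any adverse event of urticaria (medDRA preferred term) of any duration deemed related to study product". Everyone else is a non-case. No onset window is given. The figures include a "Timeline of vaccination times (grey open circles), blood draws (red points), and urticaria AE onset and resolution".

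**The concern.** Skin reactions are a recognised signal in this trial. The version history records several updates for observed skin reactions, and Section 9.1 was itself revised when urticaria follow-up was added. The dermatologic line in 9.1 nevertheless applies only to the extension, so the main study has no rule that brings in a new skin event more than 30 days after a dose for its own sake.

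SAP 10.2 takes case status from whatever was reported. It compares cases with non-cases on 16 baseline variables under a Holm adjustment, and it plots onset and resolution over study time. If late events are recorded only when they are serious, attended or lead to stopping, three things follow:

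- Some true cases may sit among the non-cases.
- Case status after day 30 depends partly on who seeks care.
- Onsets on the timeline will tend to lie near doses, in part because that is where all AEs are collected.

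The SAP does not warn the reader of any of this.

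**Working it through.** The documents give no sample size or power figure for this analysis, so there is none to reproduce. The check has four steps.

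**1. Time under full AE collection.** Inputs: doses on Days 1, 57 and 169 and final visit on Day 365 (Appendices A, B and D); a 30-day window (Section 9.1). Counting each dose day plus the 30 days after it:

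- Covered: 3 x 31 = 93 of 365 days, or 25%.
- Not covered: Days 32–56 (25), Days 88–168 (81) and Days 200–365 (166). 25 + 81 + 166 = 272 of 365 days, or 75%.

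If the dose day counts as the first of the 30, the split is 90 and 275 days, and the percentages round to the same values.

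**2. Routes open outside the window.** After dose 3 no vaccination remains to be discontinued, so that route is closed for 166 of the 272 days; withdrawal from the study remains. Hives first mentioned at a scheduled visit are not an MAAE on that ground alone. Urticaria is not an AESI. A non-serious, unattended first episode after day 30 therefore has no listed route under 9.1.

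**3. Section 9.1 against the schedules.** Days since the preceding dose: Visit 5, 43 − 1 = 42; Visit 14, 225 − 169 = 56; Visit 15, 365 − 169 = 196. The other 11 visits from Visit 02 onward lie within 30 days of a dose, counting vaccination visits as day 0. The Appendix A adverse-event row shows 13 ticks from Visit 02 on, so at least 13 − 11 = 2 fall outside the window, even allowing for uncertain column alignment. One site could record a late skin event because the schedule asks for AEs, and another could leave it out because 9.1 does not.

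**4. What misclassification could do (assumed inputs).** The documents give neither the number of cases nor the share with late onset.

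- *Chance of at least one false non-case among 108 participants*, if a proportion q have only a late, uncaptured event: 1 − (1 − q)^108. For q = 0.5%, 1%, 2% and 5% this is 42%, 66%, 89% and over 99%.
- *Effect on a comparison.* Assume a baseline factor is present in 70% of cases and 25% of true non-cases, with 8 true cases and 100 true non-cases. Odds ratio = (0.70/0.30)/(0.25/0.75) = 7.0. If 2 cases are missed, factor prevalence among 102 recorded non-cases is (100 x 0.25 + 2 x 0.70)/102 = 0.259, and the odds ratio is 6.7. If 4 are missed it is 6.4. Power by normal approximation, Φ[(difference − 1.96 x pooled SE)/unpooled SE], at an unadjusted two-sided 0.05 falls from 77% to 64% and 47%.

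In this example the odds ratio barely moves, and the loss comes mainly from having fewer cases. The SAP's Barnard tests with Holm adjustment would give different absolute values.

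**The case against.** The 30-day window is a deliberate choice and matches the primary endpoint. The extension was added later for a selected group, so closer skin follow-up there is natural. The MAAE route has no severity threshold, and the 30-day window reopens with each dose. SAP 10.2 is exploratory. The only onset range in the text of Section 2.8.1 available for this check is under 1 to 21 days, which lies inside the window. Part of that section and the study-specific procedures were not available and may say more. All of this stands, and it limits the point to a gap of unknown size.

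A reader might infer more, and four such readings are not supported:

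- *A missed recurrence makes a participant a non-case.* It cannot. Case status is per participant, so anyone with one captured related episode stays a case.
- *Someone whose late-onset hives persist to Visit 15 is a non-case.* The documents do not say so. Entry to the extension needs symptoms judged product-related, Section 8.6 records updates on related dermatological AEs, and the SAP definition has no time limit. The clearest loss is an episode that resolves before Visit 15.
- *Recorded episodes are cut short.* The 30-day rule governs which AEs are collected; it does not end follow-up of those already collected.
- *A definite share of cases, such as 5–15%, is lost, or three quarters of the risk is unobserved.* A 5–15% figure needs assumed late-onset and attendance shares that the documents do not give. The 75% is calendar time and does not measure risk.

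Long duration is not evidence of late onset either. Symptoms unresolved at Month 12 do not show that any began after day 30. The quoted range does come from COVID-19 vaccines, however, so it cannot settle the onset pattern of these first-in-human products.

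**Conclusion.** The point holds in limited form. If sites follow Section 9.1, a first related urticaria that begins more than 30 days after a dose, is non-serious and unattended, and is caught by no other route is not recorded, and the participant enters SAP 10.2 as a non-case. New recurrent episodes between day 31 and Month 12 may be missing from the timeline figure. If sites follow the adverse-event row in Appendices A and B, the event could be recorded. The loss is therefore conditional, and the unreconciled text is part of the defect.

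Full AE collection covers about 25% of main-study days. The number of participants affected cannot be derived from the documents and may be zero. The power and odds-ratio figures above show direction under stated assumptions and do not estimate the effect in this trial. The 30-day primary safety endpoint is unaffected. This is a cheap improvement to the follow-up of a known signal.

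**What to change.** **Collection.** In Protocol Section 9.1, add new or recurrent dermatologic AEs, flagged when medically attended, to the set collected through the end of the main study. State how 9.1 and the adverse-event row in Appendices A and B fit together, so that all sites apply one rule at Visits 5, 14 and 15. Days without full dermatologic collection would fall from 272 to 0. The cost is one line of text and a few more AE forms at visits already scheduled.

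**Data already collected under the 30-day rule.** Keep the SAP 10.2 case definition for the main tests, because redefining cases by onset would drop genuine late ones. Then:

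- State in SAP 10.2 that all AEs were collected only within 30 days of a dose, with limited routes outside it.
- Add a sensitivity analysis that counts as cases only onsets within 30 days of a dose and excludes later-onset cases from both groups.
- Mark the periods without full AE collection on the timeline figure.

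The cost is one extra run of tests already programmed and shading on one figure. The sensitivity analysis loses any late-onset cases that were captured, which is why it should not replace the main one.
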